The following events are considered protocol-defined AEs and should be recorded on the AE log:

1. Weight gain: 5% increase compared to baseline
2. Increased blood pressure: increase of >20mm systolic or 10mm diastolic compared to baseline
3. Increased A1c: absolute increase of 1% or greater from baseline (Screening visit value) that is sustained across 2 consecutive measures
4. Hypokalemia: any potassium value below the lower limit of normal
5. New Osteopenia (compared to Baseline): DEXA T score between -1 and -2.5
6. Osteoporosis: DEXA T score less than -2.5
7. A DEXA T score drop of ≥ -0.5 during the study

As is typical, the study will not be powered based on safety and tolerability measures because AEs are anticipated to be rare and because the type and severity of AEs may be unpredictable. **The main secondary endpoint for safety and tolerability will be a comparison of the number of serious adverse events (SAE) over the study period in the ACTH group versus the placebo group.** A SAE will be considered any event with a score equal or greater than 3 on the Common Terminology Criteria for Adverse Events (CTCAE) version 4.03. AEs receiving a mild or moderate grade will also be compared between the two treatment groups.

C. Cognition

Cognitive dysfunction is ubiquitous in MS, affecting an estimated 40-70% of patients (33), and is a major cause of disruption in daily and occupational function in MS patients (34). The most common domains of cognitive impairment in MS are memory, processing speed, visuospatial functions, verbal abilities, sustained attention and

executive function (35). The BRB-N is a set of five cognitive tests developed by National MS Society's Cognitive Function Study Group as a research tool to detect cognitive changes in MS patients and to evaluate the effect of treatment interventions on cognition (36). The five neuropsychological tests comprising the BRB-N were chosen for their ability to assess the cognitive domains most frequently impaired in MS in a practical time period (20-30 minutes). The BRB-N includes the Selective Reminding Test (SRT, a test of verbal learning and delayed recall), the 10/36 Spatial Recall Test (10/36, visuospatial learning and delayed recall), the Symbol Digit Modalities Test (SDMT, sustained attention and processing speed), the Paced Auditory Serial Addition Test (PASAT, sustained attention and processing speed) and Word List Generation task (WLG, verbal fluency).

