Low-contrast visual acuity (LCVA) is a sensitive measure of visual impairment in MS patients (40) and has been recommended for incorporation into the Multiple Sclerosis Functional Composite (MSFC). LCVA is correlated with retinal nerve fiber layer thickness as measured by OCT (41) (see section 5.F., below). Visual acuity will be measured in each eye separately as well as binocularly, at three contrast levels (100%, 2.5%, and 1.25%) using low-contrast Sloan letter charts (Precision Vision, LaSalle IL). For each measurement, the number of letters (maximum = 70) correctly identified will be recorded. Changes in LCVA over the study, and correlation of LCVA measures with OCT measures, will be exploratory outcomes of the study.

E. Fatigue

Fatigue is an extremely common symptom in MS patients, and often one of the most disabling. Over 50% (and up to 90%) of MS patients cite fatigue as a significant problem (42). The Fatigue Severity Scale (FSS) is a validated, patient-reported metric of fatigue symptoms that was specifically developed for MS and related disorders (43). The FSS will be administered to all study subjects at baseline and at each annual follow-up. The change in FSS from baseline to study end will be compared between treatment arms, as an exploratory endpoint. Many MS patients are treated with stimulant medications (such as methylphenidate, modafinil, or amphetamine preparations) for fatigue symptoms, and such medications (and the timing of their dosing) could obviously affect FSS scores, as well as other study measures. Accordingly, subjects will be asked not to take such stimulant medications on study visit days (although they will be advised to bring such medications with them, so that they may take them as needed after the study assessments are completed).

F. Global Measures of MS-related disability (EDSS and MSFC)

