The possibility of mid-study therapy regimen change for some subjects (see Exclusion criteria g. and h.) will be accounted for in analysis by running models with and without these subjects to explore the impact of these changes on analysis results. If results from the two models are consistent, all subjects will be included in the final model.

There are multiple distinct outcomes of interest in this study; since each outcome measures a unique aspect of MS progression no adjustment for multiple comparisons is planned.

Primary endpoint:

Between group differences in the odds of a 20% or greater increase in T25FW, the primary outcome measure of clinical progression of MS, will be tested at 36 months using multiple logistic regression models adjusted for covariates. Generalized

estimating equation (GEE) models will be used to test for between group differences in change over time in clinical progression (20% or greater increase in T25FW) adjusted for covariates. To test for between group differences in time to clinical progression distribution curves, Cox proportional hazards models (conditional on model assumptions being met) or Kaplan-Meier analysis will be used.

Secondary endpoints:

Safety and tolerability

To evaluate safety and tolerability of ACTH, lists and descriptive statistics of adverse events, serious adverse event, and treatment compliance will be compiled and calculated for each group at each visit. Fisher's exact tests will be used to test for between group differences in specific adverse event rates, serious adverse event rates, and treatment compliance rates.

Between group differences in mean changes in physical exam and laboratory measures (weight, blood pressure, HgbA1c, bone mineral density) will be tested using two-sample t-tests. In addition, between group differences in the proportion of subjects with abnormal blood pressure, HgbA1C, electrolyte and bone mineral density levels will be tested using Chi-square tests or Fisher's exact tests.

Change in ambulation, cognition, and global measures of MS-related disability scores

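### The supplementary test of abnormal blood pressure, HbA1c, electrolyte and bone density levels does not separate abnormality present at entry from new abnormality; the gap matters most for electrolytes

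*Combined protocol and SAP*

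**What the plan says.** Section 6.E, under Safety and tolerability, sets out three layers of analysis that bear on this point.

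- Adverse events: "Fisher's exact tests will be used to test for between group differences in specific adverse event rates", and likewise for serious adverse events and compliance.
- Mean change: "Between group differences in mean changes in physical exam and laboratory measures (weight, blood pressure, HgbA1c, bone mineral density) will be tested using two-sample t-tests". Electrolytes are not in that list.
- Abnormal levels, introduced as an addition to the mean-change tests: "the proportion of subjects with abnormal blood pressure, HgbA1C, electrolyte and bone mineral density levels will be tested", by chi-square or Fisher's exact test. Abnormal is not defined. No visit or time window is named, and nothing restricts the comparison to subjects who were normal at entry.

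Section 5.B lists protocol-defined adverse events. Most are relative to baseline. The blood pressure event is an "increase of >20mm systolic or 10mm diastolic compared to baseline". The HbA1c event is an "absolute increase of 1% or greater from baseline (Screening visit value) that is sustained across 2 consecutive measures". For bone there is "New Osteopenia (compared to Baseline): DEXA T score between -1 and -2.5", together with osteoporosis and a fall in T-score during the study. The only electrolyte event is hypokalemia, which is met by any potassium result under the lower limit of normal, whatever the screening value was.

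Section 4 excludes diabetes (including HbA1c of 6.5% or more) and osteoporosis (T-score of -2.5 or lower).

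**The concern.** The exclusions leave room for several abnormal states at randomisation: osteopenia, raised blood pressure, HbA1c below 6.5% but above whatever limit is chosen, and electrolyte abnormality. As worded, the test counts a subject who was abnormal at entry and stayed so exactly as it counts one who became abnormal on treatment. Randomisation makes the pre-existing cases equal across arms in expectation, so there is no bias towards one arm. They do shrink the difference in proportions and add variance. A non-significant result is then weaker reassurance than it looks, in a study whose sample-size section names safety and tolerability as the main objective.

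Electrolytes deserve the most attention. Section 5.B names electrolyte derangement among the adverse effects of concern. For the other three measures a reader can turn to the mean-change tests and the baseline-relative events, but for electrolytes neither exists.

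**Working it through.** **The plan's own figure.** The documents state no power for any safety comparison. The only stated figure is 42 per arm for the primary efficacy endpoint (0.6 against 0.3, two-sided 0.05, 80% power). With mean proportion 0.45:

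n = [1.960·√(2·0.45·0.55) + 0.842·√(0.6·0.4 + 0.3·0.7)]² / 0.3² = (1.379 + 0.565)² / 0.09 ≈ 42.

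It reproduces. I carry over the two-sided 0.05 level and the 50 randomised per arm.

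**Coverage, measure by measure.**

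| Measure | Excluded at entry | Mean-change test | Baseline-relative adverse event |
|---|---|---|---|
| Blood pressure | not named | yes | yes |
| HbA1c | 6.5% or more | yes | yes |
| Bone density | T-score -2.5 or lower | yes | yes |
| Electrolytes | not named | no | no |

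**Dilution.** Let b be the share abnormal at entry, assumed to persist. Let q and p be the rates of new abnormality on placebo and ACTH among subjects normal at entry.

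- As written, 50 per arm: placebo proportion b + (1-b)q, ACTH proportion b + (1-b)p. The difference shrinks to (1-b)(p-q).
- At risk only: q against p in 50(1-b) per arm.

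The documents give none of b, q or p, so all are assumptions and I show a range. Example with q = 10%, p = 30%, b = 40%: as written 0.4 + 0.6·0.1 = 46% against 0.4 + 0.6·0.3 = 58%, a difference of 12 points instead of 20. At risk only, it is 10% against 30% in 30 per arm.

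Exact two-sided Fisher power, q = 10% and p = 30%:

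| Abnormal at entry | As written: proportions | As written: power | At risk per arm | At risk: power |
|---|---|---|---|---|
| 0% | 10% v 30% | 64% | 50 | 64% |
| 10% | 19% v 37% | 44% | 45 | 58% |
| 20% | 28% v 44% | 31% | 40 | 53% |
| 30% | 37% v 51% | 24% | 35 | 46% |
| 40% | 46% v 58% | 18% | 30 | 37% |

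With a larger effect, 10% against 40%, the pairs are 93% and 93% with none abnormal at entry, 78% and 89% at 10%, 63% and 85% at 20%, 50% and 79% at 30%, and 38% and 71% at 40%.

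The at-risk test has more power at every non-zero prevalence shown, despite its smaller denominator. Because the at-risk set is defined by values taken before treatment, the comparison remains a randomised one.

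**Zero-prevalence case.** If abnormal means HbA1c of 6.5% or more, or a T-score of -2.5 or lower, the exclusions make b essentially zero and the two tests coincide.

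**The case against.** The strongest reply is that this is one supplementary test and that the plan already looks at change from baseline. That is largely right. For blood pressure, HbA1c and bone, the mean-change t-tests use baseline directly. The protocol-defined events in section 5.B are relative to baseline, or, for osteoporosis, cannot have been present at entry; they go on the adverse event log and so fall under the Fisher tests of specific event rates. The main safety endpoint, the number of serious adverse events, is untouched. What the reply does not reach is electrolytes.

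A second reply is that section 5.B says the study is not powered on safety. That stands, and no promised power is being missed. It does not justify a wording that gives up information for nothing.

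A reader might go further and infer two things that the documents do not support.

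- That power is roughly halved for all four measures. No entry prevalence is given, and the loss runs from nil to about half in the first table. It is nil for HbA1c and bone at the exclusion cut-offs.
- That the elicited-symptom questionnaire has the same defect, since it covers fatigue and section 5.E reports that "Over 50% (and up to 90%) of MS patients cite fatigue as a significant problem". The plan specifies no test that counts questionnaire symptoms regardless of the baseline answer, so this would be an inference from silence. Fatigue also has its own analysis on the Fatigue Severity Scale, adjusted for baseline score.

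**Conclusion.** The point holds for the supplementary test of abnormal levels and no wider. As worded, that test mixes pre-existing with new abnormality, and testing new abnormality among subjects at risk is a better method that uses values already scheduled. The size is conditional. With 50 per arm, persistent entry abnormality and new abnormality in 10% against 30%, the loss is 14 percentage points of power (44% against 58%) when 10% are abnormal at entry, and 19 points (18% against 37%, about half) when 40% are. With none abnormal at entry there is no loss. For blood pressure, HbA1c and bone the practical consequence is limited by the companion analyses. For electrolytes the diluted test and a hypokalemia event that ignores the screening value are all the plan offers.

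**What to change.** In section 6.E, reword the sentence so that, for each measure, the test compares the proportion with a new abnormality among subjects without that abnormality at screening or baseline. State the cut-off and the time window for each; the choice of cut-off is the sponsor's.

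For bone, define the at-risk set by category: new osteopenia or worse among subjects normal at entry, and new osteoporosis among all subjects, since none has it at entry. This keeps subjects who enter with osteopenia in the comparison that matters for them.

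Add electrolytes to the mean-change analyses, and show a baseline-to-worst shift table per arm for each measure.

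The cost is wording in the analysis plan. Table 1 already schedules the entry values: safety laboratory tests and DEXA at screening (or a recent DEXA result), blood pressure at baseline. The downside is a smaller denominator for each comparison, for example 40 rather than 50 per arm if 20% are abnormal at entry. In the cases computed above, that costs less power than the dilution does.

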ACTH is FDA-approved for treatment of MS relapses, infantile spasms, and multiple non-neurologic disorders. ACTH has both corticotropic and neurotropic properties (14), and has the potential to benefit both the inflammatory and neurodegenerative aspects of MS, respectively. Because of its corticotropic properties, long term use may result in steroid-related adverse effects (AE's). Administration of steroids as a pulsed regimen has been generally found to be well tolerated with few of the usual AEs associated with chronic corticosteroid use (12), although reduction in bone mineral density has been reported (15). The multiple mechanisms of ACTH action may offer advantages over steroids alone for the treatment of MS. Any slowing of progression resulting from treatment of progressive forms of MS with ACTH could be due to its corticotropic effects, its neuroprotective effects, and/or corticosteroid-independent effects on the immune response (16). A recent preliminary report evaluating pulsed ACTH versus pulsed MP as an add-on to interferons for treatment of RRMS found a significant benefit of pulsed ACTH (compared to pulsed MP) in reducing relapses over one year (17).

3. Hypotheses

1. ACTH administered as a monthly pulse (consisting of three consecutive days of subcutaneous injection) will be safe and well-tolerated in progressive MS patients.
2. Pulsed ACTH treatment will slow the progression of sustained physical disability of ambulation, as measured walking speed (T25FW), walking endurance (6 minute walk test, 6MWT), the Hauser ambulation index (AI), and the MS walking scale (MSWS-12), all validated measures related to ambulation in MS patients.
3. Pulsed ACTH treatment will slow the progression of sustained cognitive disability as measured by the Brief Repeatable Battery of Neuropsychological Tests (BRB-N), a measure of cognitive impairment that has been specifically validated for MS.
4. Pulsed ACTH treatment will reduce the proportion of subjects who show a sustained progression of the EDSS over the course of the study. (EDSS is a validated measure of overall MS disability).
5. Pulsed ACTH will reduce the decline in retinal nerve fiber layer thickness as measured by optical coherence tomography (OCT).

4. Inclusion and Exclusion Criteria

1. Inclusion criteria:
 - a. Male or female patients with a confirmed diagnosis of MS by McDonald criteria (18).
 - b. Age \geq 18 years.

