It should be noted that 1) the T25FW is utilized both as a stand-alone measure (and primary endpoint) and as a component of the MSFC, and 2) the PASAT is a component of both the MSFC and of the BRB-N (see section 5D, above). At each annual follow-up visit, the MSFC and the PASAT will be administered once to each subject, with the single score or measurement for that visit contributing to all relevant metrics (i.e., the PASAT will not be administered once for the BRB-N and then again for the MSFC). Previous studies have found practice effects in the 9HP and PASAT, but not the T25FW(45, 46), with the practice effects stabilizing after the third administration. Accordingly, three practice sessions of the PASAT and 9HP will be administered prior to the baseline tests. Since the PASAT is one of the components of the BRB-N, and one practice session of the entire BRB-N will be administered, two additional practice sessions of the PASAT will be administered at the screening or baseline visit. The MSFC tests will be administered according to the MSFC manual (44), including test order, instructions to subjects, testing procedures, number of repetitions, and scoring.

G. Optical Coherence Tomography (OCT)

Retinal nerve fiber layer (RNFL) thickness will be measured by OCT, an accurate and reproducible measure of the integrity of unmyelinated axons in the retina (47, 48). RNFL thickness is reduced in MS patients compared to controls, and reduction in RNFL correlates with visual function impairment in MS patients (49). The reduction in RNFL thickness is most prominent in eyes that have experienced a prior episode of optic neuritis (ON), but even eyes that have not suffered past episodes of ON show a reduction in RNFL compared to healthy controls (50). This latter fact makes OCT an attractive candidate for monitoring neurodegenerative processes in MS, which may underlie the gradual neurologic decline in progressive forms of MS. To date, limited longitudinal studies of OCT in progressive MS have been performed (51), but this remains a potentially very powerful surrogate marker for MS progression and the effect of treatments. Recently, alternative OCT measures such as macular volume and the

thickness of retinal layers other than the RNFL (e.g. the ganglion cell layer) have been shown to be abnormal in MS, and possibly to differentiate between the different MS phenotypes (52).

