Each subject will have OCT performed on each eye at baseline and then annually for 3 years (total of 4 OCT per subject). OCT will be performed on the Spectralis OCT system (Heidelberg Engineering, Germany) using the glaucoma protocol set. If the study center's available Spectralis OCT system has the neurology-oriented "N-site" software, then the RNFL scan (see below) will be obtained twice, once using the glaucoma protocol set and once using the axonal (N-site) protocol set. Pupillary dilation will not be routinely performed, as it is usually unnecessary for OCT (49). If dilation is deemed necessary to achieve adequate OCT quality (e.g., due to cataract), the subject may be excluded from the OCT portion of the study. Alternatively, dilation may be performed (with typical mydriatic eye drops) if the dilation and OCT are done after the other functional study assessments (e.g. EDSS, MSFC, LCVA, BRB-N) during the study visit, or if dilation/OCT are done on a separate visit day within a +/- 2 week window of other efficacy measures. In other words, pupillary dilation for OCT purposes will not be allowed to interfere with the other efficacy assessments that require vision for their performance.

Up to three different scans will be performed on each eye at each visit, to assess RNFL thickness, macular volume, and individual retinal layer thickness (ganglion cell layer, inner nuclear layer, etc). The RNFL scan will be obtained twice (once using the glaucoma protocol and once using the axonal protocol) if the axonal protocol is available. The axonal protocol (N-site) is optimized for detecting abnormalities in MS, and is thus the preferred method. However, all of the study sites are not expected to have access to the axonal protocol, while all will have the glaucoma protocol available. Therefore, we will obtain all scans on the glaucoma protocol (to ensure consistency of data), and acquire the axonal protocol RNFL scan as well when it is an option. The scans to be obtained are:

- i. **RNFL scan (circle scan)** – Standard settings for peripapillary RNFL with the Spectralis glaucoma protocol will be used: 12 degree (3.45 mm) circular scan manually centered on the optic disc, ART = 100, circle = 12°, 768 A-scans.
- ii. **Macular volume scan (posterior pole scan)** – The posterior pole scan from the glaucoma protocol set will be used, again using the standard settings: 30x25, 61 sections, 760 A-scans per section, distance between B-scans = 120 μ m, ART = 9.

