- iii. **(optional) RNFL scan (circle scan) using N-site software** – Standard settings for peripapillary RNFL with the Spectralis axonal protocol will be used: 12 degree (3.45 mm) circular scan manually centered on the optic disc, ART = 100, circle = 12°, 768 A-scans.

For each scan, minimum quality score is 20 (with a goal quality score of \geq 25). If a quality score of \geq 20 cannot be obtained, data from that scan will not be included for analysis. The individual centers/technicians obtaining the OCT will evaluate only for quality of the OCT scans (i.e., no

formal clinical interpretation of the OCT results will be performed. The image alignment eye-tracking system (TruTrack, Heidelberg Engineering, Germany) will be utilized throughout.

Data submitted from each OCT session will include printouts of all RNFL scans, plus electronic files (.e2e format) containing each of the 2 (or 3) scans.

If a study site does not have access to the Spectralis OCT system, a different spectral-domain high-resolution OCT system such as Cirrus HD-OCT (Zeiss) may be used as an alternative, with similar scans acquired (RNFL scan, macular volume/posterior pole).

Change in thickness of the temporal quadrant peripapillary RNFL over the course of the study will be a secondary study endpoint. Exploratory endpoints will include changes in macular volume and changes in other RNFL regions (e.g. superior, inferior, nasal, and global).

6. Statistical Issues and Data Analysis

A. Study Design

The study design is a randomized, double-blind, placebo-controlled, multi-center, phase II clinical trial.

B. Sample Size Calculation

The main objective of the study is to investigate the safety and tolerability of pulsed ACTH in progressive MS patients over three years. The primary efficacy endpoint of the study is the proportion of subjects exhibiting a 20% increase (worsening) from baseline in the T25FW. No baseline data are available regarding the rate at which a pooled population of progressive MS (i.e., SPMS, PPMS and/or PRMS) patients experience 20% increase in T25FW. However, Bosma et al. (53) evaluated change over 2 years in all three components of the MSFC (T25FW, 9HP, and PASAT) in 191 PPMS patients, and found that 45% of patients showed a 20% or greater increase in T25FW. This data was used as the basis for sample size considerations, with the following assumptions:

The findings in PPMS patients (53)

1. will generalize to a mixed sample of any progressive MS phenotype.

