2. Extrapolated to a 3 year follow up period, 60% of progressive MS patients will show a 20% or greater increase in T25FW.

Utilizing a significance level of 0.05 and equal sample sizes, 42 subjects per treatment arm would provide 80% power to detect a 50% difference in the proportion of subjects reaching the threshold of 20% worsening in T25FW ($P1 = 0.6$, $P2 = 0.3$, $\alpha = 0.05$, $\beta = 0.2$, 2-sided test). Given the length of the study, we anticipate a dropout rate of up to 10-20% of randomized subjects. To account for this possibility, a total sample size of 100 subjects (50 per treatment arm) will be randomized.

C. Randomization

The study will utilize blocked randomization stratified by study center, with equal (1:1) allocation to the ACTH and control groups.

D. Blinding

Study subjects, their referring physicians, the study monitor, and all study personnel who come in contact with study subjects (including site principal investigators, examining neurologists, study coordinators, nurses, and other study staff and their designated backups) will be blinded to treatment allocation. One investigator who will not come in direct contact with study subjects ([name]) as well as the study statistician and other members of the Data Safety Monitoring Board (DSMB, see section 7F) will be unblinded, to allow for assessment of any safety concerns that may arise over the course of the study.

E. Data Analysis Plan

Descriptive analyses of baseline characteristics and all outcome measures (primary and secondary) will include means with standard deviations or medians with ranges for continuous variables depending on the parametric or non-parametric distribution of the variables, and frequencies with percentages for categorical variables. Between group (ACTH and placebo) comparisons of baseline characteristics and baseline outcome measures will be done using two sample t-tests or Wilcoxon rank sum tests for parametric and non-parametric continuous variables, respectively, and Chi-square tests or Fisher's exact tests for categorical variables.

Models will adjust for age, gender, and MS phenotype; EDSS and disease duration will be included as covariates if significant in preliminary models. Interactions between treatment group and MS phenotype will be tested in each model; if significant, treatment effect will be evaluated in models stratified by MS phenotype.

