Between group differences in study endpoint mean of each of the secondary outcomes: change in ambulation (6MWT, MSWS-12, Hauser Ambulation Index), change in cognition (eight subtests of the five BRB-N tests), and change in MSFC z-scores will be tested using multiple linear regression models adjusted for baseline score and other covariates. Mixed model analysis of repeated measures, utilizing data collected at all time points, will be used to test for between group differences in change over time in mean secondary outcome measures adjusted for covariates. Between group differences in the odds of EDSS progression will be tested using multiple logistic regression models adjusted for other covariates. Generalized estimating equation (GEE) models will be used to test for between group differences in change over time in progression rates adjusted for other covariates. Cox proportional hazards models (conditional on model assumptions being met) or Kaplan-Meier analysis will be used to test for between group differences in time to EDSS progression.

OCT Temporal Quadrant RNFL

OCT temporal quadrant RNFL measurements from one eye per subject will be used for analysis purposes; randomly selected unless the patient has a history of optic neuritis in which case the unaffected eye will be selected. Between group differences in change in OCT temporal quadrant RNFL thickness will be tested using a multiple linear regression model adjusted for baseline thickness and other covariates. Multiple linear regression models will also be used to test for between group differences in three year rate of change adjusted for other covariates. Separate mixed model analyses of repeated

measures will be used to test for between group differences in 1) change over time in RNFL thickness and 2) change over the 3 years in annualized rates of RNFL change.

Exploratory endpoints

Fatigue

Between group differences in study endpoint mean FSS will be tested using a multiple linear regression model adjusted for baseline FSS score and other covariates. Mixed model analysis of repeated measures, utilizing data collected at all time points, will be used to test for between group differences in change over time in mean FSS adjusted for covariates.

Other vision measures

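### Temporal-quadrant RNFL is analysed in one eye per subject although both eyes are scanned every year: valid, but eligible data are discarded and a modest gain in precision is forgone

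*Combined protocol and SAP*

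**What the plan says.** Hypothesis 5 in section 3 is that pulsed ACTH slows RNFL thinning. Section 5.G gives the endpoint its rank: "Change in thickness of the temporal quadrant peripapillary RNFL over the course of the study will be a secondary study endpoint". Macular volume and the other RNFL regions are exploratory. Bone density is tested in section 6.E as a safety measure, so RNFL is the only structural efficacy measure among the secondary endpoints.

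On data collection, section 5.G says: "Each subject will have OCT performed on each eye at baseline and then annually for 3 years". On analysis, section 6.E (OCT Temporal Quadrant RNFL) takes one eye per subject, "randomly selected unless the patient has a history of optic neuritis in which case the unaffected eye will be selected". That eye enters linear regressions of change and of three-year rate, and mixed models over time.

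On covariates, section 6.E lists age, gender and MS phenotype, with EDSS and disease duration added if significant; the change regression also adjusts for baseline thickness. Centre is not listed, although section 6.C says: "The study will utilize blocked randomization stratified by study center".

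**The concern.** In a subject with no history of optic neuritis, both eyes meet the plan's own criterion, yet one is dropped by chance. Unless the two eyes change in perfect step, the dropped eye carries information about the treatment effect. The trial is sized for T25FW alone and no power is stated for RNFL, so precision here is whatever the data happen to give. The extra eye has already been scanned.

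The eye rule is also incomplete. If both eyes have had optic neuritis there is no unaffected eye to select. The history is not dated, so it is unclear whether an episode during the trial changes the choice. Eye status matters because section 5.G notes: "The reduction in RNFL thickness is most prominent in eyes that have experienced a prior episode of optic neuritis".

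**Working it through.** **The plan's own figure.** The only sample-size figure is for T25FW (section 6.B): 0.6 against 0.3, two-sided 0.05, 80% power.

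n = [1.96·√(2·0.45·0.55) + 0.8416·√(0.6·0.4 + 0.3·0.7)]² / 0.3² = (1.379 + 0.565)² / 0.09 ≈ 42 per arm.

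This reproduces the stated 42. It has no bearing on RNFL, for which no SD, effect size or correlation is given.

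**Inputs for RNFL, all assumed.** r is the between-eye correlation of RNFL change. f is the share with two eligible eyes, among subjects with at least one. Both eyes are taken to have the same variance of change and the same treatment effect.

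**Formulas.**
- Variance of a two-eye mean relative to one eye: (1 + r)/2.
- Gain in information with optimal weighting: g = f·[2/(1 + r) − 1].
- Narrowing of the confidence interval: 1 − 1/√(1 + g).

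Example, f = 0.7 and r = 0.7: g = 0.7 × (2/1.7 − 1) = 0.7 × 0.1765 = 12.4%; narrowing = 1 − 1/√1.124 = 5.7%.

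| f | r = 0.5 | r = 0.7 | r = 0.9 |
|---|---|---|---|
| 0.5 | 7.4% | 4.1% | 1.3% |
| 0.7 | 10.0% | 5.7% | 1.8% |
| 0.9 | 12.3% | 7.1% | 2.3% |

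**Where the gain becomes negligible.** Narrowing of 2% needs g = 1/0.98² − 1 = 0.0412, so r = 2/(1 + 0.0412/f) − 1 = 0.85, 0.89 and 0.91 at f = 0.5, 0.7 and 0.9.

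**Planned regressions on unweighted eye means.** The variance ratio is f(1 + r)/2 + 1 − f. Narrowing runs from 1.3% (f = 0.5, r = 0.9) to 12.0% (f = 0.9, r = 0.5).

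**Longitudinal check.** Generalised least squares with known covariance, four annual visits, 96 subjects, 15% leaving after month 12 or 24, f = 0.7 and no failed scans gave narrowing of 10.1–10.3%, 5.9–6.1% and 2.0–2.3% at r = 0.5, 0.7 and 0.9. This agrees with the closed form.

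**Validity.** Simulated type I error, 40 per arm, 4,000 runs (Monte Carlo SE about 0.34 points):

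| Analysis | r = 0.5 | r = 0.8 |
|---|---|---|
| One eye | 5.5% | 5.0% |
| Mean of both eyes | 5.4% | 5.1% |
| Two eyes treated as independent | 11.6% | 14.3% |

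One eye is valid. Two eyes are valid only if their correlation is respected.

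**Optic neuritis in both eyes.** If a share b is left out, the interval widens by 1/√(1 − b) − 1: 2.6% at an assumed b = 5%, 5.4% at 10%. If instead these subjects are kept and the effect in their eyes is k times that in unaffected eyes, the test statistic changes by the factor (1 − b + bk)/√(1 − b), assuming roughly equal subject weights. This is below 1 when k is under about 0.49. Keeping them can therefore help or hurt.

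**Failed scans.** With an assumed failure rate of 5% or 10% per scan, independent between visits, the chosen eye lacks its baseline or month-36 scan in 1 − (1 − q)² = 9.75% or 19.0% of subjects in the change regression. In the planned one-eye mixed model, variance rises only by 1.1–2.1% or 2.7–4.8%.

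**The case against.** The strongest defence is that one eye per subject is prespecified and valid, avoids the between-eye correlation altogether, and targets the eyes section 5.G regards as informative about degeneration. The gain rests on figures the documents do not supply and may be trivial. All of that stands. It limits the size of the point but does not remove it, because the extra data are collected anyway.

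A reader might infer more than the documents support:

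- **That the one-eye analysis is biased or invalid.** It is not; the simulation shows nominal type I error.
- **That the missing rule for optic neuritis in both eyes breaks intention to treat.** Section 7.F makes inclusion conditional on available efficacy data, and section 5.G already lets a subject be left out of the OCT part. Leaving subjects out on history that predates randomisation costs precision but does not bias the comparison.
- **That such subjects must be put in the main analysis.** That would admit affected eyes only in bilateral cases, depart from the unaffected-eye target of section 6.E, and lose power if the effect in those eyes is below about half.
- **That failed scans or optic neuritis during the trial are a serious threat.** Section 5.G says of a scan below the quality limit that "data from that scan will not be included for analysis", and names no fellow-eye substitute. The mixed models keep that eye's other visits, however, and section 7.D expects relapses to be quite rare. These are wording points.

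One limit on the remedy also stands: type I error was simulated for a single change score, not for the full longitudinal two-eye model with estimated covariance.

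**Conclusion.** The point holds as one of efficiency. The plan discards eligible eyes at random, and using them would narrow the RNFL interval by about 1% to 12% over the assumed ranges, or under 2% if the two eyes change nearly together. The direction is not in doubt for any r below 1, under equal variance and a common effect in the two eyes; the size is assumed. The missing centre term and the undefined case of optic neuritis in both eyes are worth settling in the same edit. Severity is minor: one secondary endpoint, with no effect on the primary result.

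**What to change.** In section 6.E, OCT Temporal Quadrant RNFL:

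1. Make the main analysis a mixed model of all quality-passing eyes with no optic neuritis before randomisation. Model the correlation between eyes within subject and state the covariance structure. Adjust for that eye's baseline thickness, the listed covariates and centre (2 degrees of freedom with the three named sites).
2. In the planned change and three-year-rate regressions, use the mean over the subject's included eyes that have the needed scans. Where baseline is adjusted for, use the baseline mean of the same eyes.
3. Keep the planned one-eye analysis as a sensitivity analysis.
4. Classify eyes by optic neuritis history at randomisation, so that selection cannot depend on later events.
5. Keep the main analysis on unaffected eyes. Report how many subjects had earlier optic neuritis in both eyes, and add them only in a sensitivity analysis with an indicator.

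The matching-eye correlation of LCVA with OCT needs no change. The cost is SAP wording and one more variance component to estimate; there are no new scans or visits, and no planned analysis is removed. The downside is little return if r is high or f is low.
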